#### **Electric Fitting:**

The participants will be fit with Nucleus Freedom for Hybrid sound processor (or most current combined speech processor) speech processor using a behind-the-ear (BTE) controller or body level controller. Speech processing strategies used with this device will include ACE (RE), ACE, CIS (RE), CIS or SPEAK, which are all FDA approved for adults. Threshold (T) and comfort (C) values will be measured for the electrical stimulation for each of the channels (22 on the Nucleus Hybrid L24 cochlear implant and 10 on the Nucleus Hybrid S12 cochlear implant). Impedance telemetry results using common ground (CG) and monopolar (MP1, MP2 and MP1+2) stimulation modes will also be recorded. This information will be used to program the speech processor and also to monitor the device for possible degradation of function and/or damage to neural elements.

The process of adjusting the speech processor programs might take place over a period of several months for younger children. Play audiometry or standard audiometric techniques will be used, as appropriate for the child's developmental level, to determine electrical threshold levels for the channels in a child's program.

Subjects will receive extensive counseling regarding how the equipment functions, maintenance and troubleshooting of the device.

#### **Acoustic Fitting:**

The acoustic component of the Hybrid sound processor will be appropriately fit using the NAL-NL1 for adults and DSL for children and adolescents (as used preoperatively for the acoustic hearing aids) to assess the degree to which real-ear targets are met for each subject. Fitting methodology with the acoustic component of the Hybrid sound processor is unchanged from that of conventional acoustic hearing aids.

The basic programming approach will be to assign frequency channels to the Hybrid electrode array that supplement the acoustic sensitivity. In other words, the frequency assignment of the electrical stimulation will begin at the frequency where acoustic hearing is no longer useful. For this purpose, hearing thresholds greater than 90 dB HL will be considered not useful from an amplification perspective and not aidable acoustically. For example, if the subject's hearing in the implanted ear is more than 90 dB HL for frequencies at and above 1000 Hz (i.e., useful acoustic hearing up to 750 Hz), the lower frequency boundary for electric stimulation will be set as close as possible to 750 Hz (i.e., the last aidable frequency). That is, electrical stimulation will be provided for inputs from around 750 to 8000 Hz and acoustic for frequencies at and below 750 Hz. Thus, there will be minimal overlap between the acoustic and the electric signals.

#### 2.4.2 Programming Follow-up

Following surgical implantation of the device and an adequate healing period, the implants will be activated (usually 4 to 6 weeks after surgery) and programmed. However, prior to the 4-month post-operative evaluation, additional programming follow-up sessions will be scheduled at 2 weeks and 1 month as it is not unusual for threshold and comfort levels to change during the initial postactivation period. The follow-up sessions will allow the participant's T- and C-levels to be checked as well as any programming adjustments to be made based on the participant's initial experience with the device. Electrical impedance measures also will be obtained. Additional programming at additional post-activation intervals will be assessed and conducted as needed.

C-levels will never be set above 200CL on any electrode. If stimulation at 200CL with the default pulse width of 25us does not elicit a maximal loudness percept, the audiologist will widen the pulse width on that channel and resume psychophysical measurements approximately 5CL below an approximately equal charge level. This will entail manually reducing the current level in the following manner:

When pulse duration is increased from:	The audiologist will manually decrease the CL from 200CL to:
25us to 37us	170CL
25us to 50us	155CL
37us to 50us	175CL
50us to 75us	170CL

Parents and professionals working with the children who participate in this study will receive extensive counseling regarding how the equipment functions, maintenance and troubleshooting of the device, and progression of auditory skills of children who cochlear implants. This is accomplished during visits to the center and through in-service training offered locally via the fiberoptic teleconferences.

#### 2.4.3 Audiologic Follow-up

##### Audiological Testing:

Unaided audiometric thresholds will be obtained for each ear, with insert earphones whenever possible, using the standard audiometric technique for pure-tone air-conduction testing. During the first month after activation of the Hybrid implant, subjects will be seen on a weekly basis to measure residual acoustic hearing. If more than a 10 dB downward threshold shift is identified, oral prednisone 1mg/kg once a day for 7 days will be prescribed. If hearing is regained or continues to fluctuate, the treating physician and the patient would discuss another trial with the prednisone. If after use of the prednisone there is no change in hearing, the prednisone will be stopped. Additional audiologic follow-up will occur at intervals of 3, 6, 12, and 24 months in adults and at intervals of 4, 8, 12, 18, 24 months, and annually thereafter for three years in children and adolescents.

Unaided (and aided if necessary) testing, for both ears, will include the following:

- Unaided Air Conduction thresholds at 125, 250, 500, 750, 1000, 1500, 2000, 3000, 4000, 6000, and 8000 Hz;
- Bone conduction thresholds at 125, 250, 500, 750, 1000, 1500, 2000, and 4000 Hz;

- Aided Air Conduction thresholds at 125, 250, 500, 750, 1000, 1500, 2000, 3000, and 4000 Hz;

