## **2.4 Postoperative Procedures**

### **2.4.1 Device Activation**

One day prior to activation, subjects without a contraindication to glucocorticoid therapy will be started on prednisone 1mg/kg for 1 week. Subjects will be asked to undergo weekly audiometric testing for one month to monitor acoustic hearing. If drops in threshold of 15 dB HL or more at 125, 250, or 500 are observed, additional prednisone 1mg/kg will be prescribed for 14 days with a gradual taper off over the following week.

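### Sections 2.4.1 and 2.4.3 give two unreconciled prednisone rules for the same first-month audiograms: a low-frequency drop of 15 dB or more can call for 7 days under one and 14 days plus a taper under the other

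*Protocol*

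**What the plan says.** Section 2.4.1 (Device Activation) begins with a preventive course: "One day prior to activation, subjects without a contraindication to glucocorticoid therapy will be started on prednisone 1mg/kg for 1 week". It then sets the monitoring, "Subjects will be asked to undergo weekly audiometric testing for one month to monitor acoustic hearing", and a rule for what the monitoring shows. The trigger is "If drops in threshold of 15 dB HL or more at 125, 250, or 500 are observed" and the response is "additional prednisone 1mg/kg will be prescribed for 14 days with a gradual taper off over the following week".

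Section 2.4.3 (Audiologic Follow-up, under Audiological Testing) sets monitoring again: "During the first month after activation of the Hybrid implant, subjects will be seen on a weekly basis to measure residual acoustic hearing". Its rule is "If more than a 10 dB downward threshold shift is identified, oral prednisone 1mg/kg once a day for 7 days will be prescribed". Two follow-on sentences apply. On a repeat course: "If hearing is regained or continues to fluctuate, the treating physician and the patient would discuss another trial with the prednisone". On stopping: "If after use of the prednisone there is no change in hearing, the prednisone will be stopped".

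Neither section mentions the other. Nothing assigns the two rules to different populations, devices or visits, and both apply to adults and to children from 5 years.

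**The concern.** Both rules are worded as instructions: in each, the prednisone will be prescribed. Discussion between physician and patient enters 2.4.3 only for a second course. If one audiogram satisfies both triggers, the protocol orders two different treatments for it, and following either section departs from the other. Two clinicians could treat the same finding differently, and a monitor could not say which of them complied.

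What is at stake is first the dose of an oral steroid, including in children. Second, the drug is given in response to loss of the residual low-frequency hearing that the implant is meant to spare and that the hybrid and combined listening conditions use. With up to 15 adults and up to 30 children and adolescents, a description of hearing preservation or of steroid exposure would be harder to read if clinicians did follow different rules. The protocol gives no evidence on whether they would.

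**Working it through.** The protocol gives no figure to reproduce. The check sets the rules side by side and then adds up the doses.

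**1. The two rules**

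| | Section 2.4.1 | Section 2.4.3 |
|---|---|---|
| Monitoring | weekly for one month, in the activation section | weekly in the first month after activation |
| Size of change | at least 15 dB | more than 10 dB, no upper limit |
| Frequencies | 125, 250 or 500 (Hz implied) | none named |
| Dose | 1 mg/kg, frequency of dosing not printed | 1 mg/kg once a day |
| Length | 14 days, then a taper over the next week | 7 days, no taper stated |
| Reference audiogram | not named | not named |

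**2. Do the triggers overlap?** Since 15 > 10, a drop of at least 15 dB at one of the three low frequencies is also a shift of more than 10 dB. This needs two conditions that the protocol does not state: both changes are measured from the same audiogram, and the 2.4.3 shift may be at a single frequency. Without them the overlap can fail:

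- *Different references.* Suppose 2.4.1 is measured from the preoperative audiogram and 2.4.3 from the previous week. A loss of 5 + 5 + 5 = 15 dB over three weeks meets 2.4.1, but no weekly step exceeds 10 dB.
- *Averaging.* Suppose the 2.4.3 shift is a mean over 125, 250 and 500 Hz. A drop of 15 dB at 125 Hz alone gives (15 + 0 + 0)/3 = 5 dB, which does not meet 2.4.3.

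**3. Is there room for a lower tier?** If thresholds are recorded in 5 dB steps (an assumption; the protocol says only that standard technique is used), the first recordable change above 10 dB is 15 dB. At 125, 250 and 500 Hz the two triggers are then the same event, and 2.4.3 would have cases of its own only at other frequencies. With finer steps, a low-frequency shift above 10 but below 15 dB would belong to 2.4.3 alone.

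**4. Size of the difference where both rules apply** (2.4.1 read as daily dosing)

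- Section 2.4.3: 7 days × 1 mg/kg = 7 mg/kg.
- Section 2.4.1: 14 days × 1 mg/kg = 14 mg/kg, plus about 7 days of taper. The taper adds between 0 and 7 mg/kg; a linear one adds (7+6+5+4+3+2+1)/8 = 3.5 mg/kg. Total 14 to 21 mg/kg (17.5 if linear).
- Ratio: 14/7 = 2 to 21/7 = 3 (17.5/7 = 2.5 if linear).
- Length: 7 days against 14 + 7 = about 21 days.
- With the preventive week (7 days, 7 mg/kg) added to each: 14 days and 14 mg/kg against 28 days and 21 to 28 mg/kg.

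At assumed weights, the added course for a 20 kg child is 20 × 7 = 140 mg against 20 × 14 = 280 to 20 × 21 = 420 mg. For a 70 kg adult it is 490 mg against 980 to 1470 mg.

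The protocol gives no rate of threshold drops, so the number of participants affected cannot be stated.

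**The case against.** The strongest defence is that the rules form tiers. Section 2.4.1 is the narrower rule, with a larger change at three named frequencies; 2.4.3 is general. Letting the specific rule govern its own cases is an ordinary way to read a document. Section 2.4.3 would not be left empty even with 5 dB steps: candidacy covers 125 to 1500 Hz, and the fitting example in 2.4.1 treats 750 Hz as useful acoustic hearing. This stands as a possible reading. It is not written, though: 2.4.3 has no upper limit and names no frequency. Elsewhere the authors do restrict a threshold when they mean to; the more-than-10-dB definition under Hearing Aid Verification is confined to that purpose.

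A sequence of 7 days followed by 14 fits less well. Section 2.4.3 makes a second course a matter for discussion, whereas 2.4.1 makes the 14 days automatic, and its added course is most naturally additional to the preventive week in the same paragraph.

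The defence is right to resist three stronger inferences.

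- A reader might infer that every audiogram meeting 2.4.1 necessarily meets 2.4.3. That holds only with a common reference and a single-frequency trigger, and the protocol fixes neither. Section 2.5 uses a three-frequency average for low-frequency loss, and Hearing Aid Verification asks for two or more frequencies, so a single-frequency reading cannot be taken for granted.
- A reader might infer that, if hearing is unchanged after a week, one section orders a stop and the other orders continuation. The stopping sentence gives no day, and the 2.4.3 course ends at 7 days anyway, so it may mean only that the course is not repeated.
- A reader might infer that the efficacy comparison is compromised. Success is defined in 2.7 and 2.8 by speech perception, localization and music, with speech and language added in children. Nothing in the text shows that clinicians alternate regimens or that a bias would run in any direction.

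**Conclusion.** The concern holds as an unreconciled dosing instruction. On the plain reading (same reference audiogram, change at a single frequency), a drop of 15 dB or more at 125, 250 or 500 Hz in the first month attracts both courses, and the text does not say which prevails. The difference in length, about 21 against 7 days, comes straight from the document. The factor of 2 to 3 in cumulative dose also assumes daily dosing in 2.4.1 and depends on the shape of the taper. The milligram figures rest on assumed weights.

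This should be corrected because it governs drug exposure in children as well as adults and because compliance cannot be judged as the text stands. It changes no sample size or error rate, and the pre- versus postoperative comparison remains valid. It is a contradiction between two stated rules rather than a detail left for an analysis plan.

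**What to change.** State one first-month rule in 2.4.1 and replace the rule in 2.4.3 with a reference to it. In the same sentence name the reference audiogram (preoperative or at activation, for the sponsor to decide) and say that a change at any single listed frequency is enough.

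If tiers are intended, write them without overlap or gap:

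- a drop of 15 dB or more at 125, 250 or 500 Hz leads to 14 days plus the taper;
- any other shift of more than 10 dB leads to 7 days. This includes a low-frequency shift above 10 but below 15 dB, and a shift only at 750 Hz or above.

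Every shift of more than 10 dB then falls in exactly one tier, whatever step size the audiometer uses.

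Say whether the stop for unchanged hearing applies to the 14-day course, and whether stopping needs a taper. State that the 2.4.1 dose is daily, if it is. Record the trigger, dates and dose of each course.

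The cost is wording and a few recorded items, with no added visit, test or participant. The real cost is the choice: the shorter course may under-treat a true drop, and the longer one raises steroid exposure, including in children. Participants already treated keep the course they had, so the records should show which rule each course followed.

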#### Hearing Aid Verification:

A hearing aid check will be completed by the clinician to verify that the contralateral hearing aid and the acoustic component of the Hybrid sound processor for the implanted ear, if used, are functional prior to aided testing. If any significant change in unaided thresholds is noted then the amplification fitting(s) should be re-evaluated and adjustments made if necessary. A significant change for this purpose only is defined as a shift of more than 10 dB (for the better or worse) at two or more (i.e., < 90 dB HL) frequencies. Hearing aid verification will occur at intervals of 3, 6, 12, and 24 months in adults and at intervals of 4, 8, 12, 18, 24 months and annually thereafter for three years in children and adolescents.

#### 2.4.4 Post-operative Testing: Population 1 (Adults)

Testing will be assessed longitudinally 3, 6, 12, and 24 months. Descriptions of tests are provided in the baseline testing section.

##### 2.4.4.1 Speech Perception Testing

Tests will be attempted in the following conditions (unless otherwise noted):

- Electric stimulation alone (Implant only),
- Hybrid stimulation (i.e., Implant + Ipsilateral Hearing Aid),
- Bimodal stimulation (i.e. Implant and Contralateral Hearing Aid)
- Combined stimulation (i.e., Implant + Ipsilateral and Contralateral Hearing Aids).

1. The CNC Word recognition test (two lists per condition, at 60 dBA).
2. The AzBio sentence lists. Two lists of the AzBio sentences will be presented at a target presentation level of 60 dBA with a +5 dB signal-to-noise ratio or SNR (i.e., the competitor will be set to 55 dBA).
3. A Speech Reception Threshold (SRT) test. Tested only at 6 months and 24 months post-operatively in the Combined and Bimodal Conditions.

Care must be taken to plug the contralateral ear, or provide contralateral masking, when a hearing aid is removed for a test condition (e.g. electric stimulation alone).

##### 2.4.4.2 Localization Testing

1. Everyday Sounds Localization test attempted in the combined and bimodal conditions at 60 dBA (tested only at 6 months and 24 months post-operatively).

##### 2.4.4.3 Music Perception

1. Real World Melody Recognition (CMR-R). This test is administered in the hybrid condition only at 70 dBA to reduce the possibility of a learning effect from repeated exposure in the same test session.
2. Modified Melodies Test: Nudge 2 (MMT). This test is administered in the hybrid and CI-only condition at 70 dBA.
3. Complex-Tone Pitch Discrimination (CTPD). This is a brief test (5-10 minutes) that can be repeatedly administered in multiple conditions accurately. This test is administered in the hybrid and CI-only condition at 70 dBA.

4. Iowa Test Appraisal of Sound Quality (ITASQ). This test is administered in the combined condition only at 70 dBA to reflect responses associated with the subject's everyday listening condition.

#### 2.4.5 Post-operative Testing: Population 2 (Children and Adolescents)

Testing will be assessed longitudinally at 4, 8, 12, 18, 24 months and annually thereafter for three years in children and adolescents.

Descriptions of tests are provided in the baseline testing section.

##### 2.4.5.1 Speech Perception Testing

Tests will be attempted in the following conditions (unless otherwise noted):

- Electric stimulation alone,
- Hybrid stimulation (i.e., Implant + Ipsilateral Hearing Aid),
- Combined stimulation (i.e., Implant + Ipsilateral and Contralateral Hearing Aids).

1. Phonetically Balanced-Kindergarten (PB-K) word test in quiet. Testing will be administered at 60 dBA to children between the ages of 5-6 years.

2. Consonant-Nucleus-Consonant monosyllabic words (CNC) in quiet. Two lists of CNC words will be administered in each test condition. Testing will be administered at 60 dBA to children between the ages of 7-15 years.

3. Computer-assisted Speech Perception Assessment Test (CASPA) in noise. Testing will be administered to children and adolescents between the ages of 7-15 years at 65 dBA speech level with a +10 signal to noise ratio.

Care must be taken to plug the contralateral or ipsilateral ear, or provide contralateral masking when acoustic stimulation is not warranted (e.g. testing CI-Only or Hybrid conditions).

##### 2.4.5.2 Localization Testing

1. Everyday Sounds Localization test attempted in the combined and bimodal conditions at 60 dBA (tested only at 12 months and 24 months post-operatively).

##### 2.4.5.3 Speech and Language Testing – all administered in the bilateral listening condition at 12 months and annually thereafter.

All tests will be administered in the combined stimulation condition, unless otherwise noted.

1. Peabody Picture Vocabulary Development Scale (PPVT)
2. Goldman Fristoe Test of Articulation (GFTA)
3. Woodcock Reading Mastery Test (WRMT-R/NU)
4. Comprehensive Assessment of Spoken Language (CASL)

##### 2.4.5.4 Music Perception

1. Complex-Tone Pitch Discrimination (CTPD). This is a brief test (5-10 minutes) that can be repeatedly administered in multiple conditions accurately. It is administered in the hybrid and CI-only condition at 70 dBA.

2. Melody Recognition by Information Level (MRIL). This test is administered in the only hybrid condition at 70 dBA to reduce the possibility of a learning effect from repeated exposure in the same test session.

#### 2.4.6 Psychophysical and Electrical Impedance Measurements:

The following psychophysical and electrical impedance measurements will be attempted at 3, 6, 12, and 24 months in adults and at 4, 8, 12, 18, 24 months and annually thereafter for three years in children and adolescents.

1. Electrical thresholds measured in current level.
2. Electrical maximum comfort levels measured in current level.
3. Impedance telemetry results using common ground (CG) and monopolar (MP1, MP2, MP1+2) stimulation modes.

#### 2.5 Adverse Effects

Adverse effects are any undesirable clinical or medical occurrence associated with use of the device or participation in the study. Any adverse effects are to be reported to the FDA and our IRB via the "Adverse Effects Form". The Primary Investigator will be required to verify that there are or there are no adverse effects to report.

Adverse effects will be reported if observed, even if acknowledged as risk factors in the consent. Adverse effects include:

1. Sudden changes in residual low-frequency hearing. Specifically, a PTA at 125, 250, 500 HZ that is  $\geq 30$  dB HL.
2. Total loss of residual hearing
3. Vertigo, dizziness, or balance problems that did not exist preoperatively or worsened postoperatively
4. Facial nerve problems
5. Meningitis
6. Perilymphatic fistulae
7. Tinnitus that did not exist preoperatively or worsened postoperatively
8. Implant Migration/Extrusion
9. Skin flap problems
10. Device-related/programming problems
11. Infection requiring explantation
12. Device failure requiring explantation

